### 7.3. Interventions

#### 7.3.1. Methylnaltrexone dosage and treatment duration

To ensure standardization of the protocol, patients with AP will be treated with methylnaltrexone or placebo intravenously for the first 5 days of admission and assessments of endpoints will be done at fixed time points during this period. The dosage will be weight adjusted. Thus, 0.15 mg/kg methylnaltrexone or a corresponding volume of matching placebo (Ringer's lactate) will be dissolved in 1000 mL Ringer's lactate solution and given as a continues infusion over 24 hours using an infusion pump. In accordance with the summary of product characteristics for methylnaltrexone, a 50 % dose reduction will be made for patients with an eGFR below 30 ml/min/1,73m^2. the continuous infusion of study medication will be started no later than 24 hours after preparation. This will be ensured by keeping detailed record on the time of preparation

as well as time of infusion start. As methylnaltrexone is sensitive to light, the solution will be kept protected from light from the time of preparation until the time of infusion start. Two persons trained in the protocol and delegated to do so, will prepare the solution of study medication together. This will be done with one person assisting virtually in exceptional cases.

#### 7.3.2. Discontinuation or withdrawal from the study

If the treatment-responsible doctor should at any point during the study assess that the patient suffers from end-stage renal impairment requiring dialysis, the treatment with methylnaltrexone will be discontinued.

Furthermore, a participant should be withdrawn from trial, if at any time:

- It is the wish of the participant for any reason
- The investigator judges it necessary due to medical reasons

If a participant is withdrawn from the trial, the investigator should always ensure that:

- Case report form (CRF) end of trial pages should be completed for withdrawn participants
- Any serious adverse events still ongoing after ended trial will be followed until the event has been resolved or the investigator assesses them as chronic or stable

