## 7.5. Participant timeline

### 7.5.1. Study days

A detailed description of the study procedures is illustrated in Table 1. Patients will be evaluated daily during admission by medical personnel and treated in agreement with the IAP/APA evidence-based guidelines for the management of AP (2). As part of the study, they will receive daily infusions with methylnaltrexone or matching placebo, and have the following examinations performed: i) clinical outcome and patient symptoms will be evaluated by means of both well-validated questionnaires and information from the patient's medical records (see section 9.1.2.), ii) the PASS score will be obtained daily and used to document the primary endpoint 48 hours after randomization, iii) blood samples (including C-Reactive Protein (CRP), interleukin (IL)-6, IL-8, IL-18, tumor necrosis factor alpha (TNF- $\alpha$ ) and cluster of differentiation 163 (CD163)) will be drawn

daily with the purpose of evaluating the systemic inflammatory response, and iv) an abdominal contrast-enhanced CT study will be performed at inclusion and after conclusion of treatment at day 5 (+/- 1 day) to document the presence and extent of pancreatic inflammation, fluid collections and necrosis according to the definitions given in the revised Atlanta criteria (20). As an integrated part of the CT exam at day 5 (+/- 1 day) patients will undergo assessment of the colon/gut transit time using radiopaque markers given orally in the morning on day 3 up to the planned CT exam. Finally, the intestinal permeability will be evaluated by a polyethylene glycol (PEG) 400/4000 test (see section 9.1.5.) 48 hours after randomization. At hospital discharge, patients are invited for a follow-up visit on day 14 (+/- 2 days) after randomization where the outcomes assessed during hospital admission (blood test and questionnaires including the PASS score) will be reassessed. Patients ready for discharge prior to completing five days treatment with methylnaltrexone will be handled according to the following:

- < 48 h of treatment: All data collection will be terminated upon discontinuation of the study medication and participant is regarded as dropout.

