### 8.2. Blinding

The study is double-blinded, and the blinding will be conducted by the Hospital Pharmacy at Herlev Hospital. This way of blinding will ensure that personnel involved in the project and participants included in the study are prevented from knowing information that might lead to bias of the results. All study medication will be labelled indicating “study medication”, “id”, “initials”, “period”, “daily dosing paradigm” and “contact information”. Labelling will be performed by the Hospital Pharmacy at Herlev Hospital, according to Annex

13 of the Good Manufacturing Practice guidelines of the European Commission, ICH, GCP guidelines, and local law.

In case of an medical emergency (e.g. SUSAR, see section 10.2.3.) that necessitates knowledge of the treatment randomization, the individual treatment assignment for each subject will be available at each study center in sealed envelopes (provided by The Hospital Pharmacy) stored in a secure area accessible to study personnel allowed by the investigator to open the code for a single subject. The other study centers can always get in contact with the primary study center by a provided phone number in case of a situation where unblinding is necessary. This procedure allows unblinding of individual subjects, without revealing codes of the entire study. Thus, the study personnel will be able to determine which treatment a particular subject was given by opening the sealed envelope with the corresponding randomization number. The investigator must state the reason why the code was broken on the envelope, date and sign it.

A subject that discontinues will be asked about the reason(s) for discontinuation and the presence of any adverse events but are not obliged to provide this information. If needed, they will be seen and assessed by a medical doctor affiliated with the study. Dropouts will be replaced by new subjects and a mirror randomization will be performed i.e. they are part of the same randomization, but with a new number (e.g. 101 replaces 1 etc.).

Patients with AP will be admitted while participating in the study and hence have the study medication (Relistor® or matching placebo) administered to them by medical professionals. The medication and placebo will be delivered to the medical staff from the Hospital Pharmacy at Herlev Hospital in the form of fluid for infusion with similar appearance, so that the medical staff treating the patient will remain blinded.

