2.5. Specification of endpoints

The primary outcome at the primary endpoint will be analyzed by intention-to-treat (ITT), whereas the secondary endpoints will be per-protocol (PP) analyses. Several factors such as treatment effect of methylnaltrexone and possible side-effects (17) may lead to an uneven distribution between excluded patients in the treatment groups (e.g. if methylnaltrexone patients are discharged earlier or discontinue treatment due to side effects). The ITT-analysis will protect against the potential bias of excluding patients unevenly according to which treatment they received. Only if the participant is randomized but never receives treatment, will they be excluded from the ITT-analysis.

The PP-analysis aims to uncover the treatment effect under ideal conditions in terms of treatment duration and follow-up. Furthermore, the PP-analysis is expected to provide mechanistic insights into the role of opioids and opioid antagonism in acute pancreatitis. Participants are included in the PP-analysis, when:

1. > 75 % of the study drug has been given
2. No major protocol deviations have been recorded

The trial is designed as a superiority trial, and we expect to see an effect of treatment after 48 hours of treatment – which is the explanation for choice of primary endpoint. Thus, we expect that the group allocated to the methylnaltrexone treatment, compared to the usual care group, will have:

1. Reduced disease severity (lower PASS-scores, lower prevalence of severe disease)
2. Improved clinical outcomes (lower pain scores, shorter admission lengths, reduced mortality, inflammatory cytokines/intestinal permeability/transit times closer to normal range, reduced prevalence of pancreatic complications)

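### Protocol 7.3.2 writes a medical decision as withdrawal from the trial and plans no PASS afterwards, so for stops before 48 hours the ITT analysis uses a carried-forward score

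*Protocol*

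**What the plan says.** Protocol 7.3.2 treats two situations differently. If dialysis becomes necessary, "the treatment with methylnaltrexone will be discontinued"; nothing is said about leaving the trial. The next rule begins "Furthermore, a participant should be withdrawn from trial, if at any time" and gives two triggers: the participant's own wish, and "The investigator judges it necessary due to medical reasons".

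For withdrawn participants the section then asks for two things: "Case report form (CRF) end of trial pages should be completed for withdrawn participants", and "Any serious adverse events still ongoing after ended trial will be followed until the event has been resolved" or is judged chronic or stable. It does not mention PASS or any other outcome.

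Four other places bear on these patients:

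- **Early discharge.** Protocol 7.5.1 says of patients ready for discharge with under 48 hours of treatment: "All data collection will be terminated upon discontinuation of the study medication and participant is regarded as dropout". SAP 6.3 repeats the rule.
- **Replacement.** Protocol 8.2 says: "Dropouts will be replaced by new subjects and a mirror randomization will be performed". SAP 3.2 defines a dropout as anyone with less than 48 hours of study medication and gives no reason as a condition. Protocol 9.3.1 ends the trial at 90 full datasets.
- **Analysis set.** SAP 2.5 excludes from ITT only randomized participants who never receive treatment. It expects that side effects may make stops uneven between arms, and says: "The ITT-analysis will protect against the potential bias of excluding patients unevenly according to which treatment they received".
- **Missing values.** Protocol 9.3 and SAP 6.3 carry the last observation forward. SAP 6.3 defends this because most missing values should come from early recovery. If many come from severe disease, it will consider other methods, which it does not name.

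**The concern.** ITT protects against uneven stopping only if the outcome is observed after the stop. Here the plan keeps the patient in the analysis set but makes no provision to collect the value that the analysis needs. The patients concerned are not those going home well. They are patients for whom the investigator saw a medical reason to stop, and most will still be in hospital.

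PASS is scheduled at baseline, 24 and 48 hours. For a stop before 48 hours, the carried-forward value is the baseline or 24-hour score. If the patient worsened after that score, the imputed value is too low. The reason SAP 6.3 gives for carrying forward, low disease activity after recovery, does not apply. If such stops are more frequent in one arm, the 48-hour comparison is biased in favour of that arm.

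The same patient also meets the SAP 3.2 definition of a dropout and is replaced. The documents do not say how a replaced patient who was treated, and so belongs in the ITT set, stands in relation to the 90 full datasets.

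**Working it through.** **1. The plan's own figure.** Inputs from Protocol 7.6 and SAP 3.1: difference 25, SD 40, two-sided alpha 0.05, power 80%.

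n per group = 2 × [40 × (1.960 + 0.842) / 25]² = 40.2, rounded up to 41. This reproduces the plan. The increase to 45 allows for 4/45 = 8.9% dropouts. Power by the normal approximation is 84.2% at 45 per group and 80.8% at 41. Because dropouts are replaced, the issue is bias rather than power.

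**2. What happens to a treated patient, by time of stop.** Five days are taken as 120 hours of infusion. The per-protocol set (SAP 2.5) needs more than 75% of study drug, which is 0.75 × 120 = 90 hours.

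| Medical withdrawal | 48-hour PASS | ITT set | Replaced (SAP 3.2) | Per-protocol set |
|---|---|---|---|---|
| Before 48 h | No collection planned; carried forward from baseline or 24 h | In | Yes | Out (at most 48/120 = 40% of drug) |
| For example at 60 h | Already recorded | In | No | Out (60/120 = 50% of drug) |

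The primary value is affected only in the first row.

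**3. Size per patient (illustration).** Protocol 9.1.1 scores organ failure at 100 points per system. Assume a patient's true 48-hour PASS exceeds the carried-forward score by 100 to 200 points, that is, one or two new organ failures. With 45 per arm, the arm mean is understated by:

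- 100/45 = 2.2 points, and 2.2/25 = 9% of the design effect
- 200/45 = 4.4 points, and 4.4/25 = 18%
- three such patients in the same arm: 300/45 = 6.7 to 600/45 = 13.3 points, or 27% to 53%

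**4. Effect on the test (illustration).** Assume no true difference, SD 40, 45 per arm and a simple two-group comparison at 48 hours. The standard error is 40 × √(2/45) = 8.43. For a shift b, the rejection probability is Φ(b/8.43 − 1.96) + Φ(−b/8.43 − 1.96).

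- Four patients in one arm, none in the other, 100 points each: b = 400/45 = 8.9, or 36% of 25. The probability is about 18% instead of 5%.
- Four in one arm and two in the other: b = 200/45 = 4.4. The probability is about 8%.
- Equal numbers and equal worsening in both arms: b = 0.

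The numbers of patients and the amounts of worsening in steps 3 and 4 are assumptions. The documents give neither.

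**The case against.** The case against is substantial, and several stronger readings fail.

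- **A reader might infer that these patients are lost from the ITT analysis.** They are not. SAP 2.5 keeps every treated participant in the set. What is missing is the observed value.
- **A reader might infer that later outcomes are also lost to ITT.** Secondary endpoints are planned as per-protocol (Protocol 9.3, SAP 2.5). Both rows of the table in the working fall outside that set. Extra blood, questionnaire or CT data from these patients would enter no planned secondary comparison.
- **A reader might infer that complications after withdrawal go unrecorded.** Protocol 10.2.1 registers adverse events for 45 hours after study medication stops; for a stop at 20 hours, that runs to hour 65. Protocol 10.2.3 provides safety follow-up of unresolved events, and Protocol 8.2 has discontinuing subjects asked about reasons and adverse events. Stay, readmission and mortality come from records (Protocol 9.1.2), although the text does not say that this applies to withdrawn patients. None of these is a PASS score.
- **A reader might infer that every medical stop of drug means withdrawal.** Section 7.3.2 concerns the investigator's judgement that withdrawal is necessary, and dialysis is worded as stopping treatment only. The only explicit end to data collection is written for early discharge. That PASS ends after a medical withdrawal is inferred from the word withdrawn and from the short list of what remains to be done.
- **A reader might infer that the bias favours methylnaltrexone.** It does so only if unrecorded worsening is more frequent in that arm. If stops for deterioration are more frequent on placebo, the bias runs the other way.
- **The SAP foresees another method** if many missing values come from severe disease. The provision is real, but it sets no threshold and names no method.

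What remains is that no text in either document provides for the 48-hour PASS after a medical withdrawal, while the SAP relies on ITT to handle such stops.

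**Conclusion.** The point holds for treated patients withdrawn for medical reasons before 48 hours. Their primary value is not planned to be observed. They enter the ITT analysis with a score that may predate the worsening, and they are replaced as well. This weakens the protection that SAP 2.5 claims.

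The size cannot be derived from the documents. On the stated assumptions it is 2.2 to 4.4 points per affected patient at 45 per arm, and only an imbalance between arms biases the comparison. A few such patients in one arm would matter against a 25-point target; none, or equal numbers with equal worsening, would not. Withdrawals after 48 hours leave the primary value intact. This is an inexpensive improvement that should be made, not a flaw that invalidates the design.

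**What to change.** **Protocol 7.3.2.** Separate stopping study medication from ending data collection. State that after a medical stop the scheduled PASS is still scored, at least through 48 hours and ideally to day 5 and day 14, and that the 30- and 90-day record outcomes are still collected, unless the participant withdraws consent. The reason to go beyond 48 hours is that SAP 6.1 models PASS over the assessment time points.

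**SAP 2.5 and 3.2.** State that these patients stay in the ITT analysis with their observed 48-hour PASS even if a replacement is enrolled. Without this, new wording in 7.3.2 leaves the dropout and replacement rule untouched. State also how they count towards the 90 full datasets in Protocol 9.3.1.

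The investigator's power to withdraw a participant, and who may stop treatment and when, are unchanged. Only data collection and analysis are addressed.

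**Cost.** An amendment to the wording, an end-of-treatment CRF page distinct from the end-of-trial page, and a little more data collection and entry. According to the SAP section 5 table, PASS comes from medical records plus self-reported pain and tolerance of solid food, and most of these patients will still be inpatients at 48 hours.

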#### 7.3.3. Adherence

Patients with AP will be admitted during study participation. Thus, medication or placebo will be administered at fixed time points by medical professionals and subsequently registered within the patient's medical records as well as in the CRF.

#### 7.3.4. Concomitant medication and care

Patients participating in the study will receive supportive treatment according to the IAP/APA evidence-based guidelines for the management of AP (2) as prescribed by the treatment-responsible physician. This includes supportive therapy with intravenous fluid therapy (Ringer's lactate 5-10 ml/kg per hour), enteral feeding (elemental or polymeric enteral nutrition formulations via nasojejunal or nasogastric route, alternatively parenteral if nasojejunal tube feeding is not tolerated) and analgesics. As the patients will be admitted during participation in the study, all concomitant medication and care will be registered in the patient's medical files as with any other patient and subsequently transferred to the CRF. This specifically includes a detailed quantification of the need for analgesics (separated into opioids and non-opioids) as this is of great clinical significance.

## 7.4. Outcomes

### 7.4.1. Primary endpoint

Difference in Pancreatitis activity scoring system (PASS) score between the methylnaltrexone group and the placebo group 48 hours after randomization

### 7.4.2. Secondary endpoints

- Difference in daily **PASS scores** between subgroups
- Difference in daily assessments of circulating **pro- and anti-inflammatory markers** (including CRP, IL-6, IL-8, IL-18, TNF- $\alpha$  and CD163) as well as **intestinal barrier markers** between subgroups
- Difference in **intestinal permeability** between subgroups measured from 48 to 72 hours after randomization using the oral polyethylene glycol 400/4000 test
- Difference in **intestinal motility** assessed by means of gut/colon transit using a CT-based radiopaque marker method on day 5 (+/- 1 day) between subgroups
- Difference in **pancreatic complications** (e.g. edema, fluid collections and necrosis) assessed and quantified with contrast-enhanced CT on day 5 (+/- 1 day) after randomization (20)
- Difference between subgroups in the following **clinical outcome parameters**: pain intensity and gut function (assessed by questionnaires), quantification of analgesics (separated into opioids and non-opioids), need for nutritional support, disease severity, invasive treatments, intensive care and hospital stay, as well as mortality during total hospitalization
- Difference in **health resource utilization** during hospitalization between subgroups

## 7.5. Participant timeline

### 7.5.1. Study days

A detailed description of the study procedures is illustrated in Table 1. Patients will be evaluated daily during admission by medical personnel and treated in agreement with the IAP/APA evidence-based guidelines for the management of AP (2). As part of the study, they will receive daily infusions with methylnaltrexone or matching placebo, and have the following examinations performed: i) clinical outcome and patient symptoms will be evaluated by means of both well-validated questionnaires and information from the patient's medical records (see section 9.1.2.), ii) the PASS score will be obtained daily and used to document the primary endpoint 48 hours after randomization, iii) blood samples (including C-Reactive Protein (CRP), interleukin (IL)-6, IL-8, IL-18, tumor necrosis factor alpha (TNF- $\alpha$ ) and cluster of differentiation 163 (CD163)) will be drawn

daily with the purpose of evaluating the systemic inflammatory response, and iv) an abdominal contrast-enhanced CT study will be performed at inclusion and after conclusion of treatment at day 5 (+/- 1 day) to document the presence and extent of pancreatic inflammation, fluid collections and necrosis according to the definitions given in the revised Atlanta criteria (20). As an integrated part of the CT exam at day 5 (+/- 1 day) patients will undergo assessment of the colon/gut transit time using radiopaque markers given orally in the morning on day 3 up to the planned CT exam. Finally, the intestinal permeability will be evaluated by a polyethylene glycol (PEG) 400/4000 test (see section 9.1.5.) 48 hours after randomization. At hospital discharge, patients are invited for a follow-up visit on day 14 (+/- 2 days) after randomization where the outcomes assessed during hospital admission (blood test and questionnaires including the PASS score) will be reassessed. Patients ready for discharge prior to completing five days treatment with methylnaltrexone will be handled according to the following:

- < 48 h of treatment: All data collection will be terminated upon discontinuation of the study medication and participant is regarded as dropout.
- ≥ 48 h of treatment, but discharge before day 5: Participant will be lost to follow-up on the following outcomes: daily PASS scores, blood samples, vital signs, quantification of need for analgesics, nutritional support, intravenous fluid resuscitation and antibiotics, and data will be analyzed using the Last-Observation-Carried-Forward method (see section 9.3.). The participant will be asked to complete questionnaires at home and they will be offered a follow-up CT scan in an outpatient setting on day 5 (+/- 1 day). Furthermore, they will be invited to participate in the 14-day follow-up and readmission rates as well as mortality will be registered retrospectively.

Randomization	Methylnaltrexone or placebo (0.15 mg/kg/day)				End of study	Follow-up
Baseline	24±2 hours	48±2 hours	72±2 hours	96±2 hours	120±2 hours	14±2 days
PASS	PASS	PASS	PASS	PASS	PASS	PASS
Clinical outcome	Clinical outcome	Clinical outcome	Clinical outcome	Clinical outcome	Clinical outcome	Clinical outcome
Blood samples	Blood samples	Blood samples	Blood samples	Blood samples	Blood samples	Blood samples
		Intestinal permeability		Intestinal transit time		

Computed tomography				Computed tomography	Health resource utilization
---------------------	--	--	--	---------------------	-----------------------------

**Table 1:** Participant timeline. PASS; pancreatitis activity scoring system.

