### 9.3. Statistical methods

A repeated measures linear mixed effects model will be used for the primary analysis and will include terms for treatment group, assessment time point (day after randomization), and the interaction of treatment with assessment time point. Summary statistics and trend curves of PASS scores will be provided for the individual time points, and the difference in PASS scores between groups 48 hours after randomization is considered the primary efficacy parameter. Subgroup and covariate analyses will be performed if applicable and in case differences in patient subgroups deemed clinically relevant are evident. The primary analysis will be by intention to treat and in case of early hospital discharge or other reasons for missing values, the Last-Observation-Carried-Forward method will be employed. Trends in PASS and other secondary endpoints assessed consequently during the treatment period (biochemical tests and clinical outcome parameters) are analyzed using linear random-effects models and results presented as fitted trend curves. Outcomes assessed at single time points (baseline characteristics, CT features and gut permeability) are compared using Student's t-test or non-parametric analysis for continues data as appropriate. Binary outcomes will be analyzed using Fisher's exact test. All secondary endpoints will be analyzed by per-protocol.

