6.3. Major Protocol Deviations

It is expected that a proportion of the patients included into the study, will recover before 5 days have passed and thus be discharged before completing the study protocol. In case of early discharge, data handling of both primary and secondary outcomes be stratified according to table 2:

< 48 hours of treatment	All data collection will be terminated upon discontinuation participant is regarded as dropout.
\geq 48 hours of treatment, but discharge before day 5	Participant will be lost to follow-up on the following outcomes: daily PASS scores, blood samples, vital signs. The participant will be asked to complete questionnaires at home, and they will be offered a follow-up CT scan in an outpatient setting on day 5 (+/- 1 day). Furthermore, they will be invited to participate in the 14-day follow-up and mortality will be registered retrospectively.

Table 2

For the statistical analyses, the Last-Observation-Carried-Forward method will be employed in case of early hospital discharge or other reasons for missing values. We expect most missing values to be a consequence of early discharge (~ recovering early from their disease) and thus the Last-Observation-Carried-Forward method will reflect this by carrying forward a value corresponding to low disease activity after discharge, which we find to be a fair assumption. If this is not the case, e.g. if a lot of missing values are due to severe disease, we will consider using other methods for imputation of missing values.

7. Implementation of Analysis Plan

A monitor will be allocated from the good clinical practice (GCP) unit at Aarhus and Aalborg University Hospitals, and the responsible monitor will contact and visit the principal investigator on a regular basis. The monitor will be authorized to inspect the different study records (CRFs,

Aalborg, Denmark

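### Data collection stops for patients discharged with under 48 hours of study drug, so the ITT primary analysis normally carries forward a baseline or 24-hour PASS that can predate their recovery

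*Protocol*

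**What the plan says.** The primary endpoint is PASS 48 hours after randomization (Protocol 7.4.1, SAP 2.5.1). Table 1 of the protocol schedules PASS at baseline, 24±2 hours and 48±2 hours, then daily to 120 hours and at day 14. No PASS is tied to discharge.

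For patients ready for discharge with under 48 hours of treatment, Protocol 7.5.1 states: "All data collection will be terminated upon discontinuation of the study medication and participant is regarded as dropout". The table in SAP 6.3 gives the same rule, for primary and secondary outcomes alike: "All data collection will be terminated upon discontinuation participant is regarded as dropout".

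The primary analysis is by intention to treat. SAP 2.5 allows one exclusion: "Only if the participant is randomized but never receives treatment, will they be excluded from the ITT-analysis". It chooses this set because losses may be uneven between arms, for example "if methylnaltrexone patients are discharged earlier or discontinue treatment due to side effects".

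On missing values, Protocol 9.3 says that "in case of early hospital discharge or other reasons for missing values, the Last-Observation-Carried-Forward method will be employed", and SAP 6.3 says that "the Last-Observation-Carried-Forward method will be employed in case of early hospital discharge or other reasons for missing values". The SAP defends this as "carrying forward a value corresponding to low disease activity after discharge". Should that not hold, with severe disease as the example, "we will consider using other methods for imputation of missing values".

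Protocol 8.2 and SAP 3.2 replace dropouts through a mirror randomization. Protocol 9.3.1 ends the trial at 90 full datasets. Neither document says whether a replaced patient who was treated stays in the analysis.

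**The concern.** SAP 2.5 keeps treated patients in the primary analysis so that uneven early exit cannot bias the comparison. The data stop undercuts this, because the patients remain in the denominator while their 48-hour outcome is not collected.

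The defence of carrying values forward suits a patient who leaves after 48 hours, whose primary value already exists. It need not suit one who leaves before. Entry requires at least two SIRS criteria in the preceding 24 hours (Protocol 7.2.1), and the last scheduled score may have been taken while the patient was still ill. An early recoverer can then enter the primary analysis with a score belonging to active disease.

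If methylnaltrexone speeds recovery before 48 hours, some of its best responders are scored as if they had not yet improved, and the estimate moves toward no effect. If early exit were commoner on placebo, the estimate would move in favour of the drug. Settling missing-data rules and running the analyses before unblinding (Protocol 9.3.2, SAP 7) limits choices made after seeing results, but supplies no score that was not collected.

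**Working it through.** **The plan's own figure.** Protocol 7.6 and SAP 3.1 give a difference of 25, SD 40, 80% power and two-sided alpha 0.05.

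n per group = 2 × [(1.960 + 0.842) × 40 / 25]² = 40.2, rounded up to 41, as stated. By the noncentral t distribution, power is 79.8% at 41 per group and 83.5% at the planned 45. The sample size is not in dispute.

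**Which value enters the primary analysis.**
1. Under 48 hours of treatment at discharge: collection stops (Protocol 7.5.1, SAP 6.3).
2. The patient was treated, so stays in the primary set (SAP 2.5).
3. A missing value is filled with the last observation (Protocol 9.3, SAP 6.3).
4. The scheduled observations before 48 hours are baseline and 24±2 hours (Protocol Table 1).

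The value entered is normally the baseline or 24-hour PASS.

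**Size of the shift.** Let D be the carried score minus the true 48-hour score, and k the excess number of early exits on active treatment among 45. Then

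bias = D × k / 45, and apparent difference = 25 − bias.

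Neither D nor k is in the documents; both are assumptions. D uses the PASS weights in Protocol Figure 2: 25 for one resolved SIRS criterion, 50 for two, and 90 for two plus regained solid diet (50 + 40). Power is for a two-sample t-test on raw 48-hour means, 45 per group, SD held at 40.

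| D | k | Bias | Apparent difference | Power |
|---|---|---|---|---|
| none | 0 | 0 | 25.0 | 83.5% |
| 25 | 1 | 25 × 1/45 = 0.56 | 24.4 | 81.8% |
| 50 | 1 | 50 × 1/45 = 1.11 | 23.9 | 80.0% |
| 50 | 4 | 50 × 4/45 = 4.44 | 20.6 | 67.4% |
| 90 | 1 | 90 × 1/45 = 2.00 | 23.0 | 77.0% |
| 90 | 4 | 90 × 4/45 = 8.00 | 17.0 | 51.4% |

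The row with D = 25 matters because the SIRS criteria met at entry need not all be present in the carried score.

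**Adding spread from the outdated scores.** With f = k/45, the active-arm variance becomes 40² + f(1 − f)D². Averaging it with 40² in the other arm lowers 80.0% to 79.3% (D = 50, k = 1) and 51.4% to 44.3% (D = 90, k = 4). Holding SD at 40 is therefore the milder assumption.

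**If replacements are added and replaced patients stay in.** The active arm has 45 + k patients and bias = D × k / (45 + k).
- D = 50, k = 1: 50/46 = 1.09; difference 23.9, power 80.5%.
- D = 90, k = 4: 360/49 = 7.35; difference 17.7, power 56.2%.

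**Does the planned baseline covariate help?** Analysis of covariance on baseline was simulated with baseline correlations of 0, 0.5 and 0.7, and with exits at random, among the lowest 48-hour scores, or among the lowest baseline scores (6,000 runs each). The estimated difference was 23.6 to 24.0 for D = 50, k = 1, and 16.8 to 17.1 for D = 90, k = 4. That matches the raw means within simulation error, so adjustment does not remove the shift.

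**The case against.** The strongest reply is that the documents can be read as not imputing these patients at all. Protocol 7.5.1 attaches last observation carried forward expressly to those with at least 48 hours of treatment, calls the others dropouts, replaces them, and ends the trial at 90 full datasets. That is a real tension, but nothing removes treated dropouts from the primary set, and SAP 2.5 says the opposite. Removing them would also exclude patients on a post-randomization outcome, which SAP 2.5 sets out to avoid.

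Other points, and what remains of each:

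- The stop rule counts hours of treatment and the endpoint counts hours from randomization. A patient whose infusion began late, or who stopped just short of 48 hours, could have a PASS inside the 48±2 hour window. This stands as a narrow exception.
- The SAP's fallback could cover an outdated high score, since severe disease is only its example. Granted, but it commits only to considering another method and names none.
- Much of PASS comes from medical records and might be rebuilt. Pain and diet tolerance are self-reported (SAP 5, Table 1), so a full score cannot be.
- The affected group may be small. SAP 6.3 expects some recovery before five days and gives no figure for 48 hours; neither document predicts an arm difference in exits before that point. This stands.
- The power figures rest on chosen values and a raw-means t-test, while SAP 6.1 plans a mixed model followed by a Bonferroni-corrected t-test or Mann-Whitney test. This stands too: they are illustrations, and 51.4% pairs the largest D with the largest k.
- With more early recovery on drug, the bias is toward no effect and does not create a false positive. True for that scenario; the reverse imbalance would favour the drug.

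**Conclusion.** The concern holds. As written, the plan keeps treated patients who leave before 48 hours in the primary analysis, stops collecting their data, and normally fills the primary value with a score that can predate recovery. The reason given for carrying values forward is weakest in this group. The conclusion follows from the text and does not depend on the arithmetic.

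The size and direction of any bias are unknown. They depend on the difference between arms in exits before 48 hours and on how outdated the carried scores are, and neither is documented. At the mild end of the illustration (one excess exit, 25 points too high) the cost is about half a point and power stays near 82%. Equal exits with equal excess in both arms would leave the expected difference unbiased and only add noise. The point should be fixed because the remedy is cheap and an uncollected score cannot be fully recovered at analysis.

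**What to change.** - Remove the under-48-hour data stop from Protocol 7.5.1 and SAP 6.3. Unless consent is withdrawn, record a full PASS at discharge or discontinuation for anyone leaving before 48 hours, and carry out the planned 48±2 hour assessment for anyone still in hospital.
- In the primary analysis, use the 48-hour value where available and otherwise the exit PASS, not the baseline or 24-hour score. An exit PASS is still a last value, so prespecify a sensitivity analysis by another method, for example the planned mixed model without imputation.
- State in Protocol 8.2 and SAP 3.2 that replaced patients who were treated remain in the primary set and that replacements are additional. Reconcile the 90-full-datasets rule in Protocol 9.3.1 with this. Dropping replacement altogether is optional.
- Report exits before 48 hours by arm and reason.

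The cost is a short protocol amendment, matching SAP wording, and one extra PASS per early leaver, taken before departure. Most items are already in the record; pain and diet tolerance must be asked. The primary set may exceed 90 patients.
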